6.2 Proposed Sample Size and Data Analysis

Upon FDA approval of CL12001 Rev 3.0, enrollment will be increased from 127 to 195 to allow for enrollment of subjects using FRED line extension. Sample size was determined through simulations. The sample size was chosen so that the Type I and the Type II error rates are bounded. With 155 subjects, there will be 80% posterior probability to reject the 45% OPC null hypothesis for efficacy and the 25% OPC null hypothesis for safety using one-sided tests with 5% Type I error.

Simulations were run in R statistical package (R citation) and OpenBUGS software, version 3.2.2. For each scenario, 10,000 datasets were generated in R. OpenBUGS was then used to obtain samples from the posterior distribution of each parameter and to calculate the probability of success. For each analysis, 50,000 samples were obtained from the posterior distributions after 1,000 samples were discarded.

Primary Efficacy

The primary efficacy endpoint in this study is complete occlusion of the target aneurysm and $\leq 50\%$ stenosis of the parent artery at the target IA at 12 months as assessed by angiography and in whom an alternative treatment of the target IA had not been performed. An alternative treatment is defined as re-treatment of the target aneurysm with an alternative treatment modality including open repair, endovascular placement of an additional stent or treatment of In-stent Stenosis observed at the 180 day or 12 month follow-up time-points or at an unscheduled study follow up visit.

The study is designed to compare the primary efficacy success percent to an independently derived performance goal, which is 45% for efficacy. The performance goal was obtained from a formal meta-analysis of results from studies of flow diverters during the first year after treatment. The methods and results of this meta-analysis are described in detail in the appendix. The null and alternative hypotheses are:

Null hypothesis: $P_e \leq 45\%$

Alternative hypothesis: $P_e > 45\%$,

where P_e is the proportion of subjects that are successes for the primary efficacy endpoint.

Allowing for up to 20% attrition through 12 months, a sample size of at least $N=155$ is expected at 12 months. Should the FRED percent equal 56.5%, then the sample size of 155 subjects would reject the null hypothesis with 80% power and one-sided 5% alpha level.

Primary Safety

The primary safety outcome is the percent of subjects who experience death or major stroke within 30 days of the implant or death due to a neurological cause or major ipsilateral stroke through 12 months post implant. The study is designed to compare the primary safety percent to an independently derived performance goal, which is 25% for safety. The null and alternative hypotheses are:

Null hypothesis: $P_s \geq 25\%$

Alternative hypothesis: $P_s < 25\%$,

where P_s is the proportion of subjects with primary safety endpoint events.

The performance goal used in the P100018 SSED of the Pipeline PUFs study was 20%. However, the definition used in the PUFs study did not include all death and major stroke within 30 days, only death of neurologic cause and major ipsilateral strokes, and it was only evaluated through 180 days, not 12 months. For this reason, the performance goal utilized here is slightly higher. The primary safety endpoint in this study has not been used or reported as such previously, so the magnitude of the effect of this change is unknown. For the purposes of the current study a conservative 5% adjustment is used, resulting in a 25% performance goal (20% from above + 5% conservative adjustment). Should the FRED primary safety endpoint percent equal 15%, then the sample size of $N=155$ subjects would reject the null hypothesis with >80% power and one-sided 5% alpha level.

Statistical Methods for Primary Endpoints

The primary safety and effectiveness endpoints will be analyzed using Bayes models (OpenBUGS). The proposed model is a beta-binomial model that assumes that the outcome is a Binomial variable and a uniform prior on the probability of event.

Likelihood:

The likelihood is constructed based on distributional assumptions on the safety and efficacy results of the FRED system.

With N_e and N_s being the number of evaluable subjects for the Efficacy and Safety endpoints, respectively, the number of subjects that are successes for the primary efficacy endpoint, y_e , and the number of subjects with primary safety endpoint events are assumed to follow Binomial distribution with respective rates π_e and π_s . Thus,

$$y_e \sim \text{Binomial}(\pi_e, N_e) \text{ and } y_s \sim \text{Binomial}(\pi_s, N_s).$$

Prior Distributions:

Uninformative prior distributions are assumed for the efficacy and safety rates. More precisely,

$$\pi_e \sim \text{Beta}(1,1) \text{ and } \pi_s \sim \text{Beta}(1,1).$$

For efficacy, if the one-sided 95% lower credible interval is at least 45%, then efficacy is established. For safety, if the one-sided 95% upper credible interval is no more than 25%, then safety is established. Bayes logistic models will be used to compute the credible intervals controlling for age (<55, 55-64, ≥65) gender (male, female), zone (1, 2, 3), and region (Japan vs others). If both the safety and effectiveness null hypotheses are rejected, then the study goal will be considered to be met.

The primary effectiveness endpoint is defined, such that a subject will be considered a failure if the following occurs:

- A retreatment of the target aneurysm is required at any time prior to the 12-month follow-up evaluation, failure is considered to have occurred at the time of retreatment;
- The study device is deployed and properly positioned at the target site but fails to fully occlude the aneurysm by 12 months post-procedure;

Or if

- Presence of >50% stenosis of the parent artery at the target aneurysm at 12 months.

If a subject is a failure of this endpoint for multiple elements of the composite endpoint, then the subject is treated as a failure at the time of the earliest failure for the purposes of the statistical analysis.

Statistical Methods for Secondary Endpoints

The timing of the primary efficacy component failures (incomplete occlusion of the target aneurysm, >50% stenosis of the parent artery at the target IA at 12 months as assessed by angiography, an alternative treatment of the target IA was performed), primary safety components (death or major stroke within 30 days of the implant, death due to a neurological cause, major ipsilateral stroke through 12 months post implant) as well as the secondary endpoint proportions and incidences will be presented using standard summary statistics including the incidence and 95% credible intervals. No hypothesis tests will be performed for the primary or secondary endpoint components or secondary endpoints.

Adverse Events

Additionally, other safety endpoints will also be assessed based on Adverse Events. The number of subjects and the number of adverse events per subjects will be presented for Adverse Events, unanticipated Adverse Events, Serious Adverse Events, and unanticipated Serious Adverse Events. The results will be provided by system organ class and preferred term. Narrative case summaries will be provided for each Serious Adverse Event. Two-sided 95% credible intervals will be presented for each adverse event with ≥5% incidence.

Technical Failures

Technical failure subjects will be presented separately but will be excluded from the ITT and Per Protocol populations if they did not receive the device. They will be included in the Safety population.

A FRED procedure will be categorized as a technical failure if the following occurs:

- Failed FRED Device Deployment Due to Technical Issues with the FRED Device
 - If the FRED Device enters the blood stream and cannot be deployed secondary to technical issues with the device itself (e.g., FRED Device malfunction or failure to access the target site due to the FRED Device), the Subject will be counted as enrolled with intent-to-treat. This will be considered as a secondary endpoint failure. The Subject will be maintained within the study and will not be replaced by another Subject. The Subject will be monitored for any Adverse Event for one (1) week

following the failed deployment due to a technical issue related to the FRED Device. Unless medically necessary to pursue treatment sooner, it is recommended that further attempts to treat the target aneurysm be deferred for a minimum of one (1) week so that any potential procedural Adverse Events may be monitored.

- Failed Device Deployment Due to Issues Related to the Procedure
 - If the FRED Device cannot be deployed due to any other issues related to the procedure, the Subject will be counted as enrolled but not treated and will not be considered a secondary endpoint failure. The Subject will be maintained within the study for one (1) week. Thereafter, the Subject may be replaced in the study. The Subject will be monitored for any Adverse Event for one (1) week following the failed deployment due to issues related to the procedure. If the Subject has an Adverse Event, that Subject will also have 30-day, 6-month and 12-month clinical follow-ups. An angiographic follow-up will not be required unless the clinician believes it is medically necessary. Unless medically necessary to pursue treatment sooner, it is recommended that further attempts to treat the target aneurysm be deferred for a minimum of one (1) week so that any potential procedural Adverse Events may be monitored.

Subgroup Analysis

Results for the primary and secondary endpoints will be stratified by the following subgroups:

- Location (anterior, posterior)
- Age (<55, 55-64, ≥65)
- Gender: results will be stratified by gender
- Anatomic location (zone 1, 2 and 3)
- Region (Japan, other countries)

Since it is not possible to determine any observed differences are truly due to a difference in treatment effect, any observed significant differences in outcomes ($p < 0.1$) across subgroups will be examined and compared to available literature regarding known risk effects for the subgroups.

Missing Data

In general, all analyses will be performed using the ITT analysis set, which constitutes all available cases and all available visits. Every effort will be made to get 12 month follow-up for all study patients. The primary endpoints will be analyzed first without imputing missing or incomplete data. Multiple sensitivity analyses will be performed in order to better understand the potential effect of missing or incomplete data on the conclusions for the primary endpoints. These sensitivity analyses will impute values for subjects who are event free (for the specific primary endpoint), but do not have complete data. The analysis method used on the imputed datasets will use the binary result (i.e. simple event percents).

Methods will be endpoint specific. For example, to determine the rate of major strokes, all subjects followed with major strokes reported or no major strokes observed during the defined time period will be counted in the analysis. A lifetable analysis of time to major stroke using the nominal visit will be constructed to use all available data. Other similar endpoints will be analyzed using this strategy.

Other endpoints can be imputed using Expected Mean algorithms. In general, when missing data exists, it is important to assess the impact of missing data on a statistical estimation and testing result; therefore, in addition to analyses based on all observed cases, sensitivity analyses will be performed on the primary endpoints. Multiple imputation method using logistic regression on selected demographic and baseline disease characteristics will be applied.

The best and worst case imputation approach will also be calculated. If under the worst-case approach the study hypotheses are upheld, no further imputation analyses will be performed. Additionally, a multiple imputation approach will be used. We construct a logistic regression model for the probability of failure based on baseline characteristics thought to be predictive of the event and/or of missingness. Imputed datasets will be generated and the results combined to re-test the primary study hypotheses.

Analysis by Center

In this single arm study it is not possible to assess a treatment by center interaction, given there is only one treatment. However, results will be summarized by center for the primary efficacy and safety endpoints. Additionally, an analysis will be performed to assess site homogeneity for these two endpoints.

To facilitate analysis, sites with fewer than 10 subjects may be lumped into a “virtual” or “pseudo” site. If the number of subjects in this pseudo site is large (e.g. greater than 20 subjects), then an attempt will be made to combine the small sites into multiple small sites variables based on geographic location, such that small sites in a similar geographic location are combined but that each pseudo site level created contains at least 10 subjects.

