2. Proportion of subjects in whom an alternative treatment of the target IA had not been performed within 12 months
3. Proportions of subjects with clinically acceptable aneurysm occlusion (90 %-100 %) of the target aneurysm at 12 months (+ 60 days, -30 days)
4. Incidence of $\geq 50\%$ In-Stent Stenosis(ISS)at the target IA at 12 months as assessed by angiography at an independent corelab

5. Proportion of subjects with complete occlusion of the target aneurysm on 12-month angiography(+ 60 days, -30 days)
6. Incidence of FRED System procedure related Serious Adverse Events
7. Incidence of FRED System device related Serious Adverse Events;
8. Incidence of unsuccessful delivery of the FRED device
9. Incidence of unsuccessful deployment of the FRED device
10. Incidence of migration of the FRED device at 12 months
11. Unplanned alternative treatment on the target IA within 12 months defined as re-treatment of the target aneurysm with an alternative treatment modality including open repair, endovascular placement of an additional stent or treatment of In-stent Stenosis observed at the 180 day or 12 month follow-up time-points or at an unscheduled study follow up visit.
12. Incidence of change in clinical and functional outcomes at 180 days and 1 year follow up, as measured by an ≥ 3 point increase in the modified Rankin Scale due to neurologic disability as compared to baseline
13. Incidence of major stroke, as measured by NIHSS at 12-months (and ophthalmic examination related to the target aneurysm if determined appropriate)
14. Incidence of minor stroke, as measured by NIHSS at 12-months (and ophthalmic examination related to the target aneurysm if determined appropriate)

The statistical analyses of the primary and secondary endpoints of the study will be based on imaging data that has been reviewed and assessed by an independent core lab and on trial clinical data that has been reviewed and adjudicated by the independent Clinical Events Committee (CEC).

Study Success Criteria:

The criterion for success is based on the posterior probability of the alternative hypotheses for both efficacy and safety (i.e. both efficacy and safety being met).

Efficacy Criterion

The FRED System will be declared efficacious if the posterior probability of the alternative hypothesis H_A based on the primary efficacy endpoint for is large, that is

$$P(H_A|Data) = P(\pi_e > 45\%|Data) > \pi^*$$

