3.4 SECONDARY ENDPOINTS

Secondary endpoints described in the protocol are listed below:

1. Proportion of subjects with clinically acceptable (90-100%) occlusion of the target aneurysm, $\leq 50\%$ stenosis of the parent artery at the target IA at 12 months (+ 60 days, - 30 days), as assessed by angiography, and in whom an unplanned alternative treatment of the target IA had not been performed within 12 months

2. Proportion of subjects in whom an unplanned alternative treatment of the target IA had not been performed within 12 months
3. Proportions of subjects with clinically acceptable aneurysm occlusion (90 %-100 %) of the target aneurysm at 12 months (+ 60 days, -30 days).
4. Incidence of $\geq 50\%$ In-Stent Stenosis (ISS) at the target IA at 12 months as assessed by angiography at an independent corelab
5. Proportion of subjects with complete occlusion of the target aneurysm on 12-month angiography (+ 60 days, -30 days).
6. Incidence of FRED System procedure related Serious Adverse Events
7. Incidence of FRED System device-related Serious Adverse Events;
8. Incidence of unsuccessful delivery of the FRED system implant;
9. Incidence of unsuccessful deployment of the FRED flow-diverter intra-cranial stent
10. Incidence of migration of the FRED system implant at 12 months;
11. Unplanned alternative treatment on the target IA within 12 months, defined as re-treatment of the target aneurysm with an alternative treatment modality including open repair, endovascular placement of an additional stent or treatment of In-stent Stenosis observed at the 180 day or 12 month follow-up time-points or at an unscheduled study follow up visit.
12. Change in clinical and functional outcomes at 180 days and 1 year follow up, as measured by an increase in the modified Rankin Scale compared to baseline;
13. Incidence of major stroke, as measured by NIHSS at 12 months (and ophthalmic examination related to the target aneurysm if determined appropriate).
14. Incidence of minor stroke, as measured by NIHSS at 12 months (and ophthalmic examination related to the target aneurysm if determined appropriate).

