7.6 SECONDARY ENDPOINT VARIABLES

A Bayesian analysis will be employed in assessment of secondary endpoints.

For all dichotomous secondary endpoints, the model employed to summarize the rate (π) of secondary endpoint will be similar to the model employed for the analysis of the primary endpoints. More specifically, under the prior for the rate

$$\pi \sim \text{Beta}(1,1)$$

the posterior distribution for the secondary endpoint event rate will be

$$\pi | Y, n \sim \text{Beta}(1 + Y, 1 + n - Y)$$

where n is the number of evaluable subjects and Y is the number of subjects with events. The rate of the endpoint with a 95% credible interval will be reported; both one-tailed and two-tailed intervals will be computed to be consistent with the two OPC sets. In addition to the results based on the model, raw counts and proportions will be reported.

For all continuous secondary endpoints, the Bayesian model employed to summarize the mean outcome (μ) and standard deviation (σ) of secondary endpoint will use a conjugate analysis where the point and interval estimates are numerically the same as the sample mean and sample standard deviation. More specifically, the prior for the mean and variance will be

$$p(\mu, \sigma^2) \propto \sigma^{-2}$$

the posterior distribution for the secondary endpoint mean (μ) and variance (σ^2) will be

$$\mu | Y_1, Y_2, \dots, Y_n, \sigma^2, n \sim \text{Normal} \left(\bar{Y}_n, \frac{\sigma^2}{n} \right)$$

$$\frac{(n-1)S^2}{\sigma^2} | Y_1, Y_2, \dots, Y_n, n \sim \chi^2(n-1)$$

where n is the number of evaluable subjects and Y_1, Y_2, \dots, Y_n are the data collected on the n subjects and S^2 is the sample variance. The mean and standard deviation rate of the posterior distribution of the mean and variance of the secondary endpoint with an equitailed 95% credible interval will be reported.

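### The delivery and deployment failure endpoints exclude failures attributed to the procedure, and the documents conflict on whether subjects without an implant are in the denominator

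*Protocol*

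**What the plan says.** **The endpoints.** Protocol section 5.5 lists, as item 9, "Incidence of unsuccessful deployment of the FRED device", and item 8 is the matching delivery endpoint. SAP section 3.4 has "Incidence of unsuccessful delivery of the FRED system implant" and "Incidence of unsuccessful deployment of the FRED flow-diverter intra-cranial stent". None of these is restricted by cause. The Protocol's Study Overview words the same two items the other way round, as successful delivery and successful deployment.

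**The counting rules.** Protocol section 6.2 (Technical Failures) divides failed deployments by cause.

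- If the device was in the bloodstream and the problem is ascribed to the device, the subject counts as intent-to-treat and as a secondary endpoint failure, and is not replaced. SAP section 2 repeats this.
- If the failure is ascribed to the procedure, "the Subject will be counted as enrolled but not treated and will not be considered a secondary endpoint failure". After a week of follow-up, "Thereafter, the Subject may be replaced in the study".

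**The analysis sets.** The opening of the same Protocol text says that technical failures "will be excluded from the ITT and Per Protocol populations if they did not receive the device", and then: "They will be included in the Safety population". Protocol section 6.1 and SAP section 5 limit the Safety Population to implanted subjects plus deaths from technical failure during the index procedure. The SAP's ITT definition requires only that FRED was introduced into the bloodstream. SAP section 1 says the ITT cohort is 145 subjects and identical to the Safety cohort. SAP section 2 removes subjects whose device never entered the bloodstream from every population. For dichotomous secondary endpoints, SAP section 7.6 says only that n "is the number of evaluable subjects and" Y is the number with events.

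**The concern.** An endpoint named as the incidence of unsuccessful deployment should say how often an attempt to place FRED failed. Here a subject can leave the procedure without the device and still not count as a failure, depending on whether the cause is recorded as device or procedure. That line is a matter of judgement: failure to reach the target site counts when it is blamed on FRED and does not count when it is blamed on something else about the procedure.

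The denominator is unsettled as well. If subjects without an implant are dropped, most of the events that the endpoint is meant to count leave the numerator and the denominator together. The credible interval reported for endpoints 8 and 9 would then describe something other than what their names say. This matters more because the failure list for the primary effectiveness endpoint in Protocol section 6.2 covers a device that was deployed but did not occlude the aneurysm, and does not list failed placement. Endpoints 8 and 9 are where a reader would look for that rate.

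**Working it through.** The plan gives no expected rate, threshold or count for delivery or deployment failure, so there is no stated figure to reproduce. The check has two parts.

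**1. Where a subject without an implant is counted**

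| Subject | Counted as a failure? | In the denominator? |
|---|---|---|
| Device in bloodstream, failure attributed to device | Yes (Protocol 6.2, SAP 2) | Protocol 6.2: out of ITT by one sentence, intent-to-treat by a later one. SAP 5 ITT: in |
| Device in bloodstream, failure attributed to procedure | No (Protocol 6.2) | Protocol 6.2: out of ITT, may be replaced. SAP 5 ITT: in |
| Device never in bloodstream | No, if attributed to procedure (Protocol 6.2) | In no population (SAP 2) |

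The Safety Population does not settle the matter. Protocol 6.2 puts technical failures in it, while Protocol 6.1 and SAP 5 leave out survivors without an implant.

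The second row shows the numerator problem under the SAP's own ITT set: the subject is in n but not in Y, and so is scored as a non-failure. The Study Overview wording shows the same gap. This subject is not a success and by rule is not a failure, so the two versions of the endpoint are not complements.

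**2. Size, by the SAP's model**

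SAP 7.6 gives a Beta(1,1) prior and posterior Beta(1+Y, 1+n−Y). The rate is Y/n, and the two-sided 95% credible interval runs between the 2.5% and 97.5% posterior quantiles.

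Assumptions, none of them in the documents: the 145 are all implanted; k further subjects had FRED in the bloodstream but received no implant; d of those k failures are attributed to the device.

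- All causes: k/(145+k)
- Device-attributed only, SAP ITT: d/(145+k)
- Device-attributed only, procedure-attributed subjects replaced and dropped: d/(145+d)
- Implanted only: 0/145 for any k

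| k, d | All causes | Device only, SAP ITT | Device only, others dropped |
|---|---|---|---|
| 1, 0 | 1/146 = 0.7% (0.2–3.7) | 0/146 = 0% (upper 2.5) | 0/145 = 0% (upper 2.5) |
| 3, 1 | 3/148 = 2.0% (0.7–5.8) | 1/148 = 0.7% (0.2–3.7) | 1/146 = 0.7% (0.2–3.7) |
| 5, 2 | 5/150 = 3.3% (1.5–7.6) | 2/150 = 1.3% (0.4–4.7) | 2/147 = 1.4% (0.4–4.8) |
| 10, 5 | 10/155 = 6.5% (3.6–11.5) | 5/155 = 3.2% (1.4–7.3) | 5/150 = 3.3% (1.5–7.6) |

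On implanted subjects only, 0/145 has a two-sided upper limit of 2.5% and a one-sided upper bound of 2.0%, however many attempts failed.

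Under the SAP ITT the shortfall is (k−d)/(145+k). For k = 5, d = 2 it is 3/150 = 2.0 percentage points. With d = 5 the rate is 5/150 and nothing is lost; with d = 0 it is 0/150.

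**The case against.** The strongest reply is that the SAP is sounder than the Protocol here. Its ITT set does not require an implant. It repeats neither the sentence excluding technical failures from ITT nor the clause exempting procedure-attributed failures. It says outright that device-attributed failures count. It also discloses failures elsewhere: the CEC adjudicates technical events (SAP 2), every consenting subject is accounted for (SAP 6.4), and device observations are tabulated and listed (SAP 9.2). Protocol 6.2 presents technical failures separately. Reporting device and procedure causes apart is prespecified and reasonable, and no hypothesis is tested on these endpoints.

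Much of this stands. Failures would not be hidden from the study report, and a split by cause is useful. But SAP silence does not repeal the Protocol's exemption, and the SAP names no denominator for endpoints 8 and 9. A listing elsewhere does not correct the endpoint rate and its interval.

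Two stronger readings are tempting and should be resisted.

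- *That the failure rate is zero by construction.* This follows only if the denominator is the implanted set. Even there, a procedural death from technical failure could count, and so could a failed first device followed by an implant; Protocol 13.4 requires a further device to be available. It does not follow under the SAP ITT. The stated identity of the ITT and Safety cohorts may simply record that, procedural deaths aside, no subject had FRED introduced without an implant, which would be a genuine zero. The documents do not say.
- *That five deployments failed*, because SAP section 1 gives 145 subjects and SAP section 7.2 a treated count of 140. The documents do not explain the difference, and nothing links it to deployment.

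**Conclusion.** The point holds in conditional form. Following the Protocol's rule understates the named rate whenever a procedure-attributed failure occurs, by the share of subjects with such failures when they stay in the denominator. If no such failure occurs and the SAP ITT is used, nothing is lost. Separately, the population rules contradict one another, so the denominator cannot be determined from the documents.

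The size is illustrative only. It rests on an assumed number of failures, an assumed split by cause, and on treating the 145 as all implanted. It also assumes that the exemption for a secondary endpoint failure refers to endpoints 8 and 9, which is the natural reading although the clause does not name them.

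The endpoints are descriptive (Protocol 6.2, SAP 7.6.1) and play no part in study success (SAP 3.3). This should be corrected, but it does not threaten the primary conclusion.

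**What to change.** 1. State in SAP 7.6 that endpoints 8 and 9 are computed on the SAP ITT set: all subjects with FRED introduced into the bloodstream, including those later replaced.
2. Count every subject who did not end the procedure with a delivered and deployed FRED as a failure, whatever the cause. Show the CEC-adjudicated cause (device or procedure) as a breakdown.
3. Report two further counts separately: failed first devices followed by a successful implant, and attempts that failed before the device entered the bloodstream.
4. Delete the clause in Protocol 6.2 that keeps procedure-attributed failures from being endpoint failures.
5. Reconcile the population statements in Protocol 6.1 and 6.2 and in SAP sections 1, 2 and 5, and use one wording (successful or unsuccessful) for both endpoints throughout.

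The cost is wording in two documents. Technical events are already adjudicated, and SAP 9.4 has the SAP approved before outcomes are analysed, so the change can be prespecified. The downside for the sponsor is a somewhat higher reported failure rate if procedure-attributed failures occurred.
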